5.3 Multidomain responder index

The multidomain responder score will be calculated as the total score across the following six domains (6MWT, FVC_{%pred}, Shoulder flexion, Visual acuity, and BOT-2 fine motor and BOT-2 gross motor) (Table 5.3.1).

 Table 5.3.1:
 Definition of the Minimal Important Difference for multi-domain responder analysis

Domain	Minimal important difference (MID)	References			
6MWT	23 meter AND 10% change from baseline	(Redelmeier et al. 1997), (Puhan et al. 2008), (du Bois et al. 2011), (Mathai et al. 2012), (Wraith et al. 2004), (Clarke et al. 2009), (Muenzer et al. 2006), (Harmatz et al. 2006), (BioMarin 2013)			
FVC _{%pred}	5% absolute change or 10% relative change from baseline in FVC _{%pred}	(Wraith et al. 2004), (Muenzer et al. 2006), (BioMarin 2013)			
Shoulder flexion	20 degree change of passive shoulder range of motion	(Wraith et al. 2004), (Harmatz et al. 2006), (Clarke et al. 2009), (Okuyama et al. 2010)			

Domain	Minimal important difference (MID)	References
Visual acuity	3 lines (corrected, both eyes)	(Arch-Ophthalmol 1999); (Ferris et al. 1982), (Reeves et al. 1993)
BOT-2 fine motor Fine Motor Precision: change of 0.72 Manual Dexterity: change of 1.47		(Wuang et al. 2009)
BOT-2 gross motor	Balance: 0.57 Running speed and agility:0.59	(Wuang et al. 2009)

To compute the multi-domain responder index, changes over time in each domain variable will be scored and classified as follows. In general, if the change is equal or greater than one minimal clinically important difference (MID), the score of +1 is provided. If changed negatively by one MID or greater, the score is -1. If there is no clinically significant change (>-1.0 to <1.0 MID), the score is 0. Furthermore:

- For 6MWT distance, the score +1 will be assigned when there is an increase of 23 meters or more AND a greater than 10% increase from baseline are observed, while the score -1 will be assigned when there is a decrease of 23 meters or more and a decrease of 10% or more from baseline are observed. Otherwise the score for this domain is 0.
- For FVC_{%pred}, the score +1 will be assigned when a 5% absolute increase or 10% relative increase from baseline, while the score -1 will be assigned when a 5% absolute decrease or 10% relative decrease from baseline. Otherwise the score for this domain is 0.
- For visual acuity, the score +1 will be assigned when both eyes, corrected, have 3 lines or more improvement in visual acuity scales, while the score -1 will be assigned when both eyes, corrected, declined 3 lines or more in visual acuity scales. Otherwise the score for this domain is 0. One line of improvement is defined as -0.10 of change in LogMAR scale.
- For shoulder flexion domain where there are two tests to evaluate MID: the score +1 will be assigned when at least one side (left or right) range of motion improves at least one MID or more where the other side does not decline for more than one MID. The score -1 will be assigned when both shoulder range of motion decline for more than one MID. Otherwise the score will be set as 0.
- For BOT-2 fine motor and gross motor domains where there are two tests to evaluate MID: the score +1 will be assigned when at least one test improves at least one MID or more where the other test does not decline for more than one MID. The score -1 will be assigned when both tests decline for more than one MID. Otherwise the score will be set as 0. The scaled score from BOT-2 is used to evaluate MID.

The integration of benefit will occur by summing the responses, positive, negative or zero, across all domain variables to derive the subject-specific multi-domain responder index.

If a subject is unable to reliably or safely perform a particular assessment at a visit, that domain will be scored as 0 for that visit.

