#### DIAGNOSIS AND CRITERIA FOR INCLUSION AND EXCLUSION:

Individuals eligible to participate in this study must meet all of the following inclusion criteria:

- 1. Confirmed diagnosis of MPS 7 based on leukocyte or fibroblast glucuronidase enzyme assay or genetic testing.
- 2. Willing and able to provide written, signed informed consent or, in the case of subjects under the age of 18 (or 16 years, depending on the region) or subjects who are intellectually impaired, provide written assent (if required) and written informed consent by a legally authorized representative after the nature of the study has been explained, and prior to any research-related procedures.
- 3. Willing to comply with all study procedures.
- 4. Sexually active subjects must be willing to use a highly-effective method of contraception while participating in the study and for 30 days following the last dose.
- 5. Females of childbearing potential must have a negative pregnancy test at Baseline and be willing to have additional pregnancy tests during the study. Females considered not of childbearing potential include those who have not experienced menarche, are postmenopausal (defined as having no menses for at least 12 months without an alternative medical cause) or are permanently sterile due to having hysterectomy, bilateral salpingectomy, or bilateral oophorectomy.
- 6. *For UX003 treatment-naïve subjects only*, apparent clinical signs of lysosomal storage disease as judged by the Investigator, including at least one of the following: enlarged liver and spleen, joint limitations, airway obstruction or pulmonary problems, limitation of mobility while still ambulatory.
- 7. *For UX003 treatment-naïve subjects only*, at least 5 years old at time of enrollment and with elevated uGAG excretion at a minimum of 2-fold over the mean normal levels for age (at baseline).

Individuals who meet any of the following exclusion criteria will not be eligible to participate in the study:

- 1. *If enrolled in a prior UX003 clinical study*, the subject experienced safety-related event(s) in the prior UX003 clinical study that, in the opinion of the Investigator and sponsor, precludes resuming UX003 treatment.
- 2. Undergone a successful bone marrow or stem cell transplant or has any degree of detectable chimaerism with donor cells.

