5.6 Percent predicted Six-Minute Walk Tests

To calculate the percent predicted 6MWT value, the following formulas will be applied (Geiger et al. 2007) for subjects aged <20 years old at informed consent of this study

For Males:
$$X_i = \frac{X_{0i}}{196.72 + (39.81 * Age) - (1.36 * Age^2) + (132.28 * Height)} * 100$$

For Females:
$$X_i = \frac{X_{0i}}{188.61 + (51.50 * Age) - (1.86 * Age^2) + (86.10 * Height)} * 100$$

Where:

 X_i = The percent predicted 6MWT result at time i for subject X

 X_{0i} = The 6MWT (m) result at time i for subject X

To calculate the percent predicted 6MWT value, the following formulas will be applied (Gibbons et al. 2001) for subjects aged ≥ 20 years old 15 at informed consent of this study:

$$X_i = \frac{X_{0i}}{868.8 - (2.99 * Age) + (74.7 * Women)} * 100$$

Where:

 X_i = The percent predicted 6MWT result at time i for subject X X_{0i} = The 6MWT (m) result at time i for subject X The age and height measured at corresponding visit will be used to calculate percent predicted 6MWT value.

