8.7 Efficacy Analyses

Because the primary objective of this study is to evaluate the long-term safety, the efficacy parameters will not be grouped into primary or secondary categories.

The percent change in uGAG excretion will be analyzed using the generalized estimating equation (GEE) method. Model will include baseline a covariate and visit (in this study) as a factor. The covariance structure within subjects will be assumed to be exchangeable.

Descriptive statistics will be presented by assessment time point for observed and change from baseline for the following other efficacy parameters.

- Biomarkers of inflammation in serum
- 6MWT and the percent predicted 6MWT value
- BOT-2
- 3MSCT
- Pulmonary function testing (eg., FVC, FEV and MVV1)
- Shoulder range of motion (goniometry) in extension and flexion by shoulder and the average of the right and left shoulders.
- Visual acuity
- Fatigue
- MPS HAQ
- CHAQ
- HAQ
- Scoring of impactful clinical problems
- Cardiac ventricular mass

Descriptive statistics will be presented by assessment time point for the following other efficacy parameters.

- MDRI
- Fatigue MID
- Subject/Parent/Caregiver CGI scales
- Hepatosplenomegaly

For growth, anthropometric measurements with z scores and percentiles will be summarized by historical time point and on study visit. For naïve subjects, the slopes of growth velocities will be summarized for pre (historical up to 2 years and baseline data) and post (baseline and post treatment data) treatment periods. For IST subjects, the growth velocities will be calculated for pre-initial UX003 treatment (up to 2 years) and post-initial UX003 treatment. For rollover subjects, the growth velocities will be calculated for pre first treatment in the feeder study (up to 2 years) and post first treatment in the feeder study.

For ICR, whether a positive change, according to the MID criteria, has occurred in the prespecified ICR will be assessed. The percentage of subjects achieving an ICR MID will be calculated for the rollover subjects and presented by assessment time point.

- 8.8 Safety Analyses
- 8.8.1 Adverse Events

The latest Medical Dictionary for Regulatory Activities (MedDRA) will be used to code all AEs to a system organ class (SOC) and preferred term.

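### The MDRI scores 6MWT in raw metres, so a child aged about 5–7 at baseline who only keeps pace with the SAP's own normative curve can score +1 by about Weeks 120–144

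*SAP*

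**What the plan says.** SAP 5.3 builds the MDRI as the sum of six domain scores, each +1, 0 or −1. Table 5.3.1 sets the 6MWT threshold at "23 meter AND 10% change from baseline". The text gives +1 only when "an increase of 23 meters or more AND a greater than 10% increase from baseline are observed", and −1 for a fall of at least 23 m that is also at least 10%. Both conditions apply to distance in metres.

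Three of the other five domains enter on a normed scale. FVC is percent predicted. For the two BOT-2 domains, "The scaled score from BOT-2 is used to evaluate MID", and Protocol 7.5.4.4 describes the test as norm-referenced. Shoulder flexion (degrees) and visual acuity (lines) are unadjusted.

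SAP 5.6 already derives percent-predicted 6MWT, with paediatric equations for subjects under 20 at consent: "The age and height measured at corresponding visit will be used to calculate percent predicted 6MWT value". SAP 8.7 lists "6MWT and the percent predicted 6MWT value" for descriptive summary. The MDRI is also descriptive, by time point, and does not use the percent-predicted value.

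Treatment-naïve subjects must be "at least 5 years old at time of enrollment" (Protocol synopsis, inclusion criterion 7). Their baseline is in this study. Rollover subjects keep the feeder-study baseline (SAP 5.1), and CL301 subjects enter at CL301 Week 48 (Protocol 7.5.1). The 6MWT is done at Weeks 24 and 48 and then every 24 weeks to Week 144 (Protocol Table 2.1).

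**The concern.** Young children walk further as they age and grow. When a raw distance is compared with a baseline nearly three years old, or nearly four for a CL301 rollover, part of any gain is expected from development. The SAP's own equations say how much. If that amount clears both 23 m and 10%, a child whose standing against healthy peers has not changed is scored as improved, and a child who has slipped against peers may be scored as unchanged.

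The study has a single arm of about 20 subjects, so no control group shows the developmental component. Protocol 7.2.3 presents the MDRI as an assessment of UX003 efficacy across the main clinical domains, so a shift in one direction in one domain matters to how it is read.

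**Working it through.** The plan states no expected MDRI value to reproduce. The check applies the SAP 5.6 equations to the SAP 5.3 rule.

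**Equations (predicted distance P in metres, age a in years, height h).** Boys: "196.72 + (39.81 * Age) - (1.36 * Age^2) + (132.28 * Height". Girls: "188.61 + (51.50 * Age) - (1.86 * Age^2) + (86.10 * Height". (The closing bracket is left off both.) Height is taken in metres: 110 entered as centimetres would contribute 132.28 × 110 ≈ 14,551 m.

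**Method.** Hold percent predicted constant at a fraction p. Distance then goes from p·P0 to p·P1. The percentage change is P1/P0 − 1 whatever p is. The metre change is p·(P1 − P0), so the 23 m condition needs p ≥ 23/(P1 − P0).

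**Elapsed time.** 96 weeks = 1.84 y and 144 weeks = 2.76 y. For a CL301 rollover, 48 + 144 = 192 weeks = 3.68 y, taking the feeder baseline to be CL301 Week 0.

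**Assumed heights (not in the documents).** (i) 1.10 m at age 5, growing 6 cm/year. (ii) 0.95 m at age 5, growing 3 cm/year. (iii) No growth from baseline, at either 0.95 m or the heights in (i).

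**Worked example.** Boy aged 5, 1.10 m, 6 cm/year:
- Baseline: 196.72 + 199.05 − 34.00 + 145.51 = 507.3 m.
- Week 144, age 7.76, height 1.266 m: 591.2 m.
- Change: +83.9 m, or 16.5%. The 23 m condition needs p ≥ 23/83.9 = 27%.
- At a constant 50% of predicted he goes from 253.6 to 295.6 m, and scores +1.

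**Rise in predicted distance, %, from a baseline in this study** (6 cm/year; 3 cm/year; no growth):

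| Baseline age | Week 96 | Week 120 | Week 144 |
|---|---|---|---|
| Boy 5 | 11.5; 10.4; 8.6–9.0 | 14.1; 12.8; 10.5–10.9 | 16.5; 15.0; 12.2–12.7 |
| Boy 6 | 9.9; 8.9; 7.1–7.5 | 12.1; 10.8; 8.7–9.1 | 14.1; 12.7; 10.1–10.6 |
| Boy 7 | 8.5; 7.5; 5.9–6.3 | 10.3; 9.2; 7.1–7.6 | 12.1; 10.7; 8.2–8.8 |
| Girl 5 | 12.9; 12.3; 11.0–11.3 | 15.7; 14.9; 13.3–13.7 | 18.4; 17.4; 15.5–15.9 |
| Girl 6 | 10.7; 10.1; 8.9–9.2 | 13.0; 12.3; 10.8–11.2 | 15.2; 14.3; 12.5–13.0 |
| Girl 7 | 8.9; 8.3; 7.2–7.5 | 10.8; 10.0; 8.7–9.0 | 12.5; 11.6; 10.0–10.4 |

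- Through Week 72 no case exceeds 10%. The nearest is a girl aged 5 growing 6 cm/year (9.9%), who crosses at about week 73.
- At Week 144, a boy aged 7 with no growth falls short. A girl aged 7 with no growth is borderline (9.96% at the taller height).
- The upper baseline age for +1 at Week 144 is about 8.1 y at 6 cm/year, 7.4–7.7 y at 3 cm/year, and 6.0–6.3 y (boys) or 7.0–7.2 y (girls) with no growth.
- The 23 m condition needs p of about 36% (23/63.7) to 45% (23/50.9) at Week 96, and about 25% (23/90.9) to 42% (23/54.5) at Week 144.
- At 192 weeks from a feeder baseline, every case at ages 5–7 exceeds 10% (10.2–23.2%). In-study Week 48 is already about 96 weeks from that baseline.

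**Masked decline.** For the boy in the example, −1 needs distance to fall to 0.90 of baseline. His percent predicted must then fall to 0.90/1.165 = 0.77 of baseline, a loss of about 23%. If he drops from 60% to 48% of predicted (a 20% relative loss), he goes from 304.4 to 283.8 m. That is −20.6 m and −6.8%, and he scores 0.

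**The case against.** The strongest objection is that the calculation describes healthy children. Protocol 5.1 and 5.4 describe a progressive disease with short stature and loss of walking. An untreated child with MPS 7 may not track the norm at all, and keeping percent predicted constant may itself be benefit. This stands. A reader might infer that each such +1 is a false response. The documents contain no untreated trajectory, so they show how far the normative value moves, not how much response is spurious.

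A reader might also infer that the index is inflated generally. It is not. The AND rule screens out most short walkers, nothing arises through Week 72 from a baseline in this study, and the age window is narrow. The 5-year floor is stated only for naïve subjects, and neither the age mix nor CL301's age range is given.

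A third tempting inference is that the point counts for more once BOT-2 stops at Week 48 under the current protocol. The MDRI is a sum, so +1 adds one point whether four or six domains are measured.

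Two mitigations also stand in part. The 6MWT is not the only raw-scale domain, although it is the only one of the raw-scale domains for which the SAP supplies an equation showing its threshold crossed. Percent-predicted 6MWT is summarised separately and derived data are listed by subject, so the pattern can be found. But a summary in another table does not correct the summed index.

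**Conclusion.** The point holds as a limited, directional weakness in a descriptive endpoint. By the SAP's own equations, constant percent predicted is enough for +1 at baseline ages of about 5–7 by about Weeks 120–144: from about Week 96 at age 5, and with about 3 cm/year of growth for a boy aged 7. CL301 rollovers reach it about 48 weeks sooner in study time.

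The size is at most one MDRI point per affected child. The total cannot be computed because the ages are not given. The result rests on the assumed heights and growth, on percent predicted staying constant at or above roughly 25–45%, and on the feeder baseline being about 48 weeks before entry. The direction favours apparent improvement, and the same mechanism can conceal decline against peers. That justifies a sensitivity display, not replacement of the index.

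**What to change.** Keep the metre-based MDRI unchanged. Prespecify in SAP 5.3 and 8.7, for subjects under 20 at consent, a sensitivity MDRI shown beside it at each visit. Score its 6MWT domain on the SAP 5.6 percent-predicted value: +1 or −1 when percent predicted changes by more than 10% relative to baseline and the change also equals at least 23 m at that visit's predicted distance, that is |change in percentage points|/100 × P1 ≥ 23 m. Keeping the 23 m floor matters: under a 10% rule alone, a child walking 100 m would score on a 10 m change. State that the threshold carries over the existing MID and is not separately validated, since the documents give none for percent predicted.

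Under this rule the boy at a constant 50% scores 0. The boy falling from 60% to 48% scores −1 (12 points × 591.2 m = 70.9 m).

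The cost is SAP wording, one extra table and a slightly lower MDRI for the youngest children. One limitation should be footnoted: at fixed height the equations peak at 39.81/(2 × 1.36) = 14.6 years (boys) and 51.50/(2 × 1.86) = 13.8 years (girls). In late adolescence an unchanged distance therefore raises percent predicted. For a girl aged 19 with an assumed fixed height of 1.50 m, P falls from 624.8 to 557.7 m by Week 144, a 12% rise in percent predicted. The two versions should therefore be read together.

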#### 7.5.4.6 Pulmonary Function Testing

Spirometry will not be conducted on subjects who require invasive ventilatory support or have a tracheostomy. Invasive ventilation is defined as any form of ventilatory support applied with the use of an endotracheal tube. Spirometry will be administered in accordance with ATS/ERS guidelines (ATS/ERS 2002) to appropriate subjects during the Baseline visit, then every 24 weeks thereafter (or at termination visit). Spirometry performed at the primary (or feeder) study End of Treatment visit or within 30 days prior to Baseline may be used for the study baseline. If performed on the same day, spirometry should be done before the 6MWT and 3MSCT. The subject's resting heart rate must return to baseline between assessments.

*For subjects enrolling from prior clinical studies with UX003,* Spirometry will only be administered if previously performed in their primary (or feeder) study. Spirometry performed within 30 days prior to Baseline may be used for the study baseline assessment.

Pulmonary function variables include forced vital capacity (FVC) and maximum voluntary ventilation (MVV). The percent predicted values will be calculated after testing using published normative data (Wang et al. 1993), (Eigen et al. 2001), (Hankinson et al. 1999). If standing height cannot be obtained, an estimate of standing height may be used to derive the height measurement required to calculate percent predicted values.

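### The MDRI scores a lost ability the same as no change, and the six-domain index has no value after Week 48 because BOT-2 stops there

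*SAP*

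**What the plan says.** SAP 5.3 defines the index: "The multidomain responder score will be calculated as the total score across the following six domains". The domains are 6MWT, percent-predicted FVC, shoulder flexion, visual acuity, BOT-2 fine motor and BOT-2 gross motor. Each scores +1, 0 or -1 against a minimal important difference (MID). On decline: "If changed negatively by one MID or greater, the score is -1". On stability: "If there is no clinically significant change (>-1.0 to <1.0 MID), the score is 0". On inability, the subject who is "unable to reliably or safely perform a particular assessment at a visit, that domain will be scored as 0 for that visit".

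The current protocol (Amendment 3) names the same six components in 7.5.4.1 and sets no end date for the index. Section 7.5.4.4 and Table 2.1 collect BOT-2 at Baseline, Week 24 and Week 48 only. The other four components continue at Weeks 72, 96, 120 and 144. The SAP was written to Amendment 1, and its Appendix 1 still shows BOT-2 every 24 weeks to the end.

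On missing data, SAP 7.1 and protocol 7.6.3 both leave missing values missing unless stated otherwise. SAP 8.7 reports the MDRI descriptively by time point, and the percentage of rollover subjects meeting their ICR criterion in the same way.

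**The concern.** There are two problems.

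First, the inability rule treats two different subjects alike: one who could never do the test, and one who had a usable baseline and then lost the ability. For the first, 0 is reasonable. For the second, a worse outcome than a measured decline gets a better score. The protocol makes such losses foreseeable. Section 5.1 describes loss of walking and eventual tracheostomy as part of the disease, and 7.5.4.6 states: "Spirometry will not be conducted on subjects who require invasive ventilatory support or have a tracheostomy". The SAP does not say whether spirometry omitted for that reason counts as inability (score 0) or as missing. Neither gives -1. Rollover subjects keep their feeder-study baseline (SAP 5.1), so for them the period over which an ability can be lost is longer than this study.

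Second, a composite meant to support long-term efficacy (protocol 7.5.3) has no definition that can be computed for most of the study, although four of its six parts are still measured. Any ICR mapped to BOT-2 (protocol 7.5.4.10) likewise has no data after Week 48.

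What is at stake is how the long-term summary is read. The MDRI carries no hypothesis test, so error rate, power and sample size are not involved.

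**Working it through.** **Domain count.** Counting the SAP 5.3 list gives 4 domains without BOT-2 plus 2 from BOT-2 = 6, the number the SAP states. The possible range is -6 to +6.

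**Inability rule, shown on 6MWT.** SAP 5.3 gives -1 for a fall of at least 23 m that is also at least 10% of baseline. The baseline of 300 m is assumed for illustration.

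| Visit result | Change | Score |
|---|---|---|
| 300 m | none | 0 |
| 270 m | -30 m, -10% | -1 |
| 150 m | -150 m, -50% | -1 |
| 0 m, recorded as a result | -300 m, -100% | -1 |
| Unable to perform | not measured | 0 |

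The last row equals the first and is 0 - (-1) = 1 point above a qualifying decline.

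**Effect on a visit mean.** If k of n subjects each have one lost domain scored 0 rather than -1, the mean is higher by k/n. The documents do not give k. With n = 20 (the planned enrolment, so an upper figure for subjects with an MDRI) and assumed k of 1, 2, 3 or 5, the difference is 0.05, 0.10, 0.15 or 0.25 points. A smaller n makes it larger for the same k.

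**Which domains the rule reaches.** Shoulder flexion is a passive range of motion (protocol 7.5.4.7), so it is not readily lost as an ability. BOT-2 is not collected after Week 48. In the long-term period the rule therefore mainly concerns 6MWT and FVC.

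**Visits with all components scheduled** (protocol Table 2.1 and its footnote on 24-weekly visits):

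| Weeks | Domains scheduled |
|---|---|
| 24, 48 | 6 of 6 |
| 72, 96, 120, 144 | 4 of 6 |

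The six-domain total is unavailable at 4/6 = 67% of post-baseline visits, covering 144 - 48 = 96 weeks, and 96/144 = 67% of the planned duration. A total of the four remaining domains runs from -4 to +4.

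**Does any existing rule fill the gap?** The inability rule covers a subject who cannot do a test, not a test that is no longer scheduled. The BOT-2 scoring text ends: "The score -1 will be assigned when both tests decline for more than one MID. Otherwise the score will be set as 0". That default follows conditions on observed changes, so it is most naturally read as applying to observed results. The general rule then leaves the BOT-2 domains, and with them the six-domain total, missing.

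**How the two parts interact.** On this reading the zero rule acts on the six-domain index at Weeks 24 and 48 only. It matters for Weeks 72 to 144 as soon as a four-domain or partial total is reported there.

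**The case against.** Much of the BOT-2 gap is version lag. SAP 1.0 predates Amendment 3, it defers to the protocol on study design (SAP 3), and protocol 7.6.3 requires only that the SAP be approved before lock. That stands for the SAP. It does not explain protocol 7.5.4.1, which in its current version still includes both BOT-2 domains with no time limit.

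The components are also summarised one by one, and all data are listed. This limits the harm, but the component summaries use observed data, so a subject who can no longer do a test drops out of them. No planned table counts lost abilities.

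Zero can be defended as a pre-specified neutral score. Inability at one visit may be temporary or behavioural, and scoring -1 for losses without credit for gains leans the other way. This stands, and it is why -1 belongs in a sensitivity version, not as a replacement. Losing one test of a two-test BOT-2 domain also need not change the score, because -1 already requires both tests to decline.

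A reader might infer that scores will jump at Week 72, since dropping or zeroing BOT-2 would move a subject in unchanged condition by -2 to +2 points. That happens only if BOT-2 is dropped or zero-filled. Under SAP 7.1 and protocol 7.6.3 the index simply ends at Week 48, and no value is distorted.

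**Conclusion.** Both parts hold and should be fixed before lock; neither threatens the study's primary purpose.

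- A lost ability is scored as no change, 1 point better than a qualifying decline. This follows directly from the SAP text and needs no assumption.
- The six-domain MDRI has no value at 4 of 6 post-baseline visits (96 of 144 weeks), and a BOT-2-based ICR has no data over the same period. This rests on reading the missing-data rules in their ordinary sense.

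A reader might go further and infer that the MDRI results will be materially inflated. The documents do not support that: they give no frequency of lost abilities, and the k/n figures only illustrate scale. A reader might also object that shoulder flexion, visual acuity and the BOT-2 domains need both sides, eyes or tests to decline before scoring -1. That is a separate feature of the index and is not part of this conclusion. Because the endpoint is descriptive and secondary to safety and uGAG, the consequence is confined to interpretation.

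**What to change.** Update the SAP to Amendment 3 and align protocol 7.5.4.1 with it.

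- **(a) Composition.** Use a four-domain MDRI (6MWT, percent-predicted FVC, shoulder flexion, visual acuity) at Weeks 24 to 144 as the long-term series. Limit the six-domain MDRI and any BOT-2-based ICR to Weeks 24 and 48. State that the default to 0 in the scoring rules applies to observed results only.
- **(b) Lost ability.** Keep the current 0 rule and add one sensitivity version of the four-domain MDRI. It scores -1 for a domain with a valid baseline that the subject can no longer perform, including spirometry not done because of a new tracheostomy or invasive ventilation.
- **(c) Transparency.** Report by visit the number of lost, gained and never-able domains, with the reason, since version (b) gives no credit for gains and may count temporary inability. Note that protocol 7.5.4.3 allows 6MWT to be left out after a failed Baseline, so gains there may be undercounted.

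The cost is a SAP revision, the four-domain score, its sensitivity version and one table. A CRF query may be needed to separate inability from a missed test. No new assessments are required. Values will be slightly less favourable under the sensitivity scoring where abilities are lost.
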